#### **Introduction:**

Ventricular tachycardia (VT) has become an increasingly prevalent cardiovascular condition. Factors leading to that include aging of the population, increasing use of implantable defibrillators and improved survival of patients with cardiomyopathy. VT ablation has become the cornerstone for treatment of VT. Event-free survival following the ablation procedure has been modest adding to the steep cost and associated risks. Moreover, patients with more complex scar structure and multiple VTs bear the highest likelihood of VT recurrence.

Identifying critical parts of the VT machinery is key to successful ablation and durable long-term results. VT associated with structural heart disease is usually re-entrant, utilizing areas of slow conduction and unidirectional block caused by conduction barriers. Those barriers can be further classified into structural and functional. Although there have been major strides in the use of CT and MRI for assessing scar structure, current imaging tools still offer very little in terms of functional imaging of scar, with relevance to understanding the pathophysiology of VT.

The role of the autonomic nervous system in the genesis of VT has been studied for decades.  Several techniques have been used to interrupt sympathetic input to the myocardium at the levels of the spinal cord, sympathetic chain, and renal artery.  However those measures have been reserved for the most refractory of cases given the lack of standardized techniques, and higher potential for long-term complications. There have been no reports of attempts at terminal cardiac sympathetic modulation in the setting of VT associated with cardiomyopathy in humans.

Fallavollita et al have recently shown that the magnitude of sympathetic dysinnervation associated with hibernating myocardium correlates with the risk for sudden cardiac death and fast VT requiring ICD therapies. [N-13] NH3, [18 F]-fluorodeoxyglucose (FDG), and [C-11] meta-hydroxyephedrine (MHED) were used in that study to determine the relationships between regional myocardial perfusion, metabolism and the distribution of adrenergic receptors with PET imaging. The findings in that study were in alignment with a growing body of evidence derived from studies that used 123I-metaiodobenzylguanidine (MIBG). However, that study was the first to demonstrate that PET imaging of cardiac innervation is feasible in large clinical trials. Assessing the anatomic and functional elements reflected by MHED scans, and its relationship to the genesis of VT, seems very intriguing from an electrophysiologic perspective.

Regional denervation associated with cardiomyopathy with hibernating myocardium is usually followed by a process of re-innervation, known as nerve sprouting. Several studies have demonstrated that the presence of inhomogeneity of sympathetic innervation in the setting of cardiomyopathy is associated with sudden cardiac death. Nerve sprouting induced by infusion of growth factors into the left stellate ganglion in dogs was associated with the occurrence of ventricular arrhythmias. Moreover, there is histologic evidence that VT does

originate from areas with increased density of sympathetic nerve fibers, i.e. areas with nerve sprouting. 14 Therefore, it is plausible that inhomogeneity of sympathetic innervation of scar results from areas with nerve sprouting in the background of denervated scar. The interaction of dynamic changes to spatial distribution of sympathetic innervation, its effects on electrophysiologic properties of scar, and the inhomogeneity of scar structure form the foundation to the machinery needed to sustain VT (i.e. slow conduction and unidirectional block).

Integration of PET/CT imaging of LV scar prior to VT ablation has been reported by Tian et. al.  In that study, perfusion was assessed using Rubidium-82, and metabolic activity was assessed by FDG. The authors were able to show correlation between PET and electroanatomic maps. Ahmad et. al have demonstrated that MIBG can be used to image sympathetic innervation of scar, for use during ablation of VT.  In that study, 90% of successful ablation sites were located within dysinnervated areas. Moreover, 10% of successful ablation sites existed in dysinnervated areas with normal bipolar voltage (possibly indicating healthy myocardium). This study was fraught with misalignment of the anatomic models. That would affect the validity of their conclusions and can be avoided by using CT scanning for better definition of cardiac anatomy. The crude resolution of MIBG scans is not adequate to identify more detailed regional details, which would be necessary to identify ablation targets.

Additionally, [C-11] MHED is far superior to MIBG scanning for the following reasons:

- 1. PET offers superior sensitivity and resolution over SPECT
- 2. Global down regulation of MIBG uptake in subjects with heart failure makes it hard to make accurate interpretations of MIBG scans

To date, sympathetic dysinnervation has never been assessed using PET for the purpose of guiding VT ablation procedures. Moreover, sympathetic dysinnervation has not been well studied in patients with non-ischemic cardiomyopathy, which is more challenging to manage, given the relatively more obscure substrate.

#### **Study Goals:**

- A. Demonstrate capability of producing and using the PET agent [C-11] MHED
- B. Identify the electrophysiologic properties of areas of relatively increased [C-11] MHED uptake within myocardial scar
- C. Identify correlations of preliminary imaging and electrophysiologic data for hypothesis generation. Those shall be investigated with further studies to assess impact on procedural outcomes, and event free survival after VT ablation in future larger studies.

# **Preliminary hypothesis:**

1) PET/CT imaging with [C-11] MHED can guide the identification of elements that are critical to the development of VT, which exhibit abnormal sympathetic influence.

Areas of relative increase in myocardial [C-11] MHED uptake may represent regional nerve sprouting within the background of dysinnervated scar and? represent critical elements to the substrate of VT.

2) Ablation targets detected by conventional electrophysiologic mapping techniques are likely to exist in such areas with dysinnervation, which are likely representative of nerve sprouting.

The data provided by PET/CT imaging could be used to modify the current approaches for VT ablation. Data on the regional adrenergic receptor quantity and distribution could be crucial to improving procedural outcomes and event-free survival in patients with life threatening ventricular arrhythmias.

# **Brief Protocol:**

# Study Design:

Pilot, hypothesis generating, nonrandomized study

Number of subjects: 15 patients

Duration of subject participation: Subjects will be enrolled in the study during a pre-ablation visit/consultation and participate in the study from the time consent is obtained, through the PET scan, and for 30 days following ablation. Patients are not required to attend the follow-up visit in order to be considered complete in the study.

#### Study Population:

All enrolled patients will be patients referred to Mercy cardiovascular group for consideration of ablation of ventricular tachycardia and have a clinical indication for ablation per standard of care.

#### Inclusion Criteria:

- Patients with clinical indication for VT ablation (at least one clinical episode of sustained VT) despite antiarrhythmic drug therapy, or if the patient does not wish to be on one
- 2. Ischemic or non-ischemic cardiomyopathy (will try to enroll equal number of each)
- 3. Sustained monomorphic VT is a requirement
- 4. Age 18-80 years old
- 5. Ability to provide informed consent

#### Exclusion criteria:

- 1. Right ventricular VT
- 2. Polymorphic VT or VF being the sole detected clinical arrhythmia
- 3. Pregnancy or lactation (unanticipated, pregnancy test to be done for women in the childbearing age)

#### Subject Recruitment:

Mercy clinic patients will be recruited by the Principal Investigator, Sub-Investigators, or other designated study team member. Informed consent will be obtained by the Principal Investigator or delegated study personnel. After the informed consent is obtained, the study team will provide the subject's information to the Washington University coordinator for scheduling of the PET/CT scan using the Study Subject Information Sheet by Mercy Secure File Transfer System.

Study Procedures:

Screening/Visit 1	Standard of Care + Research	Discuss ablation and its clinical indication Discuss participation in the study Obtain informed consent Determine eligibility
Optional Cardiac MRI	Standard of Care	Cardiac MRI will be done as per standard of care prior to ablation of ventricular tachycardia. Cardiac MRI is not required for participation on the study
Visit 2	Research	PET/CT scan will be done at Washington University imaging facility up to 21 days before scheduled ablation.
Visit 3	Standard of Care	Cardiac ablation procedure will be done per standard of care
Data-only follow-up	Research	Adverse event and VT recurrence data, when available, will be collected 30 days (+/- 5 days) following cardiac ablation procedure.

# Schedule of Events

Procedures	Screening /Visit 1	Optional Cardiac MRI*	Visit 2**	Visit 3	Data-only Follow-up (30 days)
Informed Consent	X				
Demographics	X				
Past Medical History	X				
Inclusion / Exclusion	X				
criteria review					
PET/CT Scan			X**		
Ablation				X	
MRI		X			
Adverse Events			X**		X
Assessment					

\* Cardiac MRI will be done as per standard of care prior to ablation of ventricular tachycardia. Cardiac MRI is not required for participation on the study.

Criteria for withdrawal of subjects and provision of care after withdrawal

- Patients may cancel participation in the study at any time without penalty. Clinical care will be provided as per standard of care.
- Patients will be removed from the study if they become ineligible at any point before or after the PET scan is performed, or if they become unable or are no longer willing to provide informed consent.

\*\* Visit 2 occurs at Washington University. Mercy PI/Mercy Research will be notified by Washington University of any adverse events occurring during Visit 2

- The investigator(s) may also discontinue or remove a participant from the study for the following:
  - o To protect the subject for reasons of safety.
  - If any clinical adverse event, laboratory abnormality, or other medical condition or situation occurs such that continued participation in the study would not be in the best interest of the participant.
  - The subject is determined no longer be able to complete study protocol visit activities.
  - Significant non-compliance by the subject with study requirements.
- The reason for participant discontinuation or withdrawal from the study will be documented.
- It will be documented whether each subject completes the study.
- Information collected up to the last visit will be included in analysis.
- Subjects who sign the informed consent but do not complete the PET/CT scan may be replaced as enrolled subjects.
- Participants who sign the informed consent form and complete the PET/CT scan and subsequently withdraw or are withdrawn or discontinued from the study will not be replaced as enrolled subjects.
- Participants who are unable to complete the PET/CT will be considered withdrawn/incomplete. Their data will be included in summary analysis but will not be used in hypothesis testing.

# **Study Evaluations and Measurements:**

Screening visit activities (i.e., informed consent and eligibility determination) must be completed within 30 days of the scheduled cardiac electrophysiology clinic evaluation and prior to Visit 1 and referral to Washington University for scheduling of the PET/CT scan. No study activity will take place until the subject has provided informed consent.

#### PET/CT:

PET/CT imaging will be performed at Washington University.

Description of tracers: C11 HED is taken up by neurons like norepinephrine and is stored in presynaptic vesicles. The C11 HED signal is an indicator of sympathetic nerve terminals in the myocardium. This tracer has been used for that purpose for decades, albeit only in research settings given its short half-life, which makes it unsuitable for mass production or transportation, etc.

Imaging is to be performed with PET/CT scanner, after injecting [C-11] MHED.

Please see the Washington University Supplemental Imaging Protocol for further details.

## Electroanatomic mapping procedure:

Electroanatomic maps will be created using mapping catheters as performed for standard of care ablation procedures.

High-density electroanatomic maps (>150 points for the LV) will be acquired using the Thermocool SmartTouch or Thermocool SF catheters or similar mapping catheters.

The areas of interest will be mapped in detail using conventional electrophysiologic techniques. Signal amplitude, electrogram characteristics (low amplitude, late, fractionated, etc.) will be noted. Entrainment mapping of VT will be pursued whenever possible.

Maps will be merged offline after the ablation case has ended, which is typically done on the mapping computers. Correlations between PET uptake values and electro-anatomic data obtained during ablation (data regularly obtained during the course of an ablation case including refractory periods, voltage measurements, roles in VT circuit) will be made as part of final data analysis.

Post-procedural follow up will be arranged for subjects based on current standards of care. Antiarrhythmic drugs will be required for, at least, the first 8 weeks unless there is a contraindication.

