#### Definition of an Adverse Event

Definitions of adverse events, serious adverse events and unanticipated problems per Mercy policies and procedures. Serious adverse events and unanticipated problems related to the PET/CT scan and tracer injection will be documented and reported for this study. Adverse event screening will begin at the beginning of visit 2 through 30 days following the ablation procedure.

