# Potential risk to Subjects:

Risks associated with the PET/CT scan include:

- -Radiation exposure
- -the radiotracer is known to have no significant physiologic effect according to published data
- -Venipuncture
- -Breach of confidentiality

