#### Recruitment Methods

Recruited subjects will be patients referred to Mercy cardiovascular group for management of ventricular tachycardia in whom ablation is determined to be the patient's preferred therapeutic option. Patients will be consented during evaluation in the cardiac electrophysiology clinic, satellite clinics or remotely. The informed consent will be obtained by the Principal Investigator or delegated study personnel. Subjects will be given as much time as they like to make a decision on whether they would like to participate in the study. The investigator will ensure that the patient understands the study's risk and benefits, etc. PI and study personnel will follow the Mercy Research SOP for informed consent including remote consent procedures.

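### Does the 8-week antiarrhythmic drug sentence conflict with enrolling patients who do not want such a drug?

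*Protocol*

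**What the plan says.** Inclusion Criteria, item 1, asks for a clinical indication for VT ablation "despite antiarrhythmic drug therapy, or if the patient does not wish to be on one". A patient may therefore enter after drug failure or because of a preference against the drug.

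The last paragraph of Electroanatomic mapping procedure turns to care after ablation. It opens with "Post-procedural follow up will be arranged for subjects based on current standards of care" and continues with "Antiarrhythmic drugs will be required for, at least, the first 8 weeks unless there is a contraindication".

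Three other places bear on how that second sentence should be read:

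- **Duration of subject participation** (Brief Protocol): subjects "participate in the study from the time consent is obtained, through the PET scan, and for 30 days following ablation".
- **Definition of an Adverse Event**: "Serious adverse events and unanticipated problems related to the PET/CT scan and tracer injection will be documented and reported for this study", and "Adverse event screening will begin at the beginning of visit 2 through 30 days following the ablation procedure".
- **Potential risk to Subjects**: the list is introduced by "Risks associated with the PET/CT scan include" and has four items, none about drugs.

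The drug appears in neither the Study Procedures table nor the Schedule of Events.

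**The concern.** A patient can be enrolled because they do not want an antiarrhythmic drug, and then meets a sentence that requires one for at least 8 weeks and excuses only those with a contraindication. No section says which text governs, or whether the sentence is a study requirement or a description of usual care.

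If it were a study requirement, several things would be out of place. The required period would run beyond both participation and adverse event screening. The schedule and the risk list would omit a mandated treatment. Serious harms from the drug would lie outside the scope that the adverse event definition names. Site staff would not know whether a refusal is a protocol deviation, or whether it could count towards the withdrawal criterion on significant non-compliance with study requirements. Under Recruitment Methods, "The investigator will ensure that the patient understands the study's risk and benefits", and it would be unclear whether the drug's risks are among them.

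What would be at stake is conduct and participant information. Results would be at stake only if a refusal removed data from the analysis or distorted an analysed outcome.

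**Working it through.** The protocol attaches no statistical figure to this point. The check is a reading of the text with a little date arithmetic.

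**1. Do the two sentences contradict each other?** Item 1 explains why a patient is a candidate for ablation. Recruitment Methods says the same in other terms: ablation is the option the patient prefers. The drug sentence concerns the weeks after the procedure. A patient can prefer ablation to drug therapy and still accept a limited course afterwards. Both sentences can hold for the same patient, and the gap is silence about a patient who then declines.

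**2. Study requirement or standard care?** The two readings compare as follows.

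| Place in the protocol | Standard care | Study requirement |
|---|---|---|
| Preceding sentence puts follow-up under current standards | fits | does not fit |
| Study Procedures labels the ablation visit standard of care; the only research item after it is data-only | fits | does not fit |
| Schedule of Events: 8 rows, 0 on drugs | fits | does not fit |
| Risk list: 4 items, 0 on drugs, and none on ablation or MRI | fits | does not fit |
| Serious-event scope tied to scan and tracer | fits | does not fit |
| The word *required*, with one exemption | fits poorly | fits |

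The risk-list row carries weight. Ablation and MRI both have rows in the Schedule of Events, yet their risks are not listed either. The section leaves out standard care in general, so silence on the drug is what the standard-care reading predicts.

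**3. The time overhang.** Inputs: 8 weeks from Electroanatomic mapping procedure, counted from ablation (an assumption, since the sentence does not name its starting point); 30 days from the participation and adverse event sections; a window of ±5 days from Study Procedures.

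- Required period: 8 × 7 = 56 days at least.
- Beyond day 30: 56 − 30 = 26 days; 26/56 = 46%.
- Collection at day 35: 56 − 35 = 21 days; 21/56 = 38%.
- Collection at day 25: 56 − 25 = 31 days; 31/56 = 55%.

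These figures describe a gap only if the drug is a study treatment. Standard care need not end inside a 30-day research window.

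**4. Can a refusal affect the results?**

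- The PET/CT scan is done up to 21 days before ablation and the maps are made during it. Both precede the drug period.
- The withdrawal criteria keep information collected up to the last visit in the analysis. The exclusion from hypothesis testing concerns participants who could not complete the PET/CT.
- VT recurrence at 30 days could depend on drug use. It is collected only when available, the Analysis section plans nothing with it, and the Study Goals leave event-free survival to later, larger studies.

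The number entering by preference is not given. Over its whole range, 0 to 15, the effect on the PET and mapping correlations is nil.

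**The case for a change.** The strongest case for a change is that the wording is not that of description. It sets a minimum duration and names one exemption. The Study Procedures table labels other standard care, including the optional MRI and the ablation, and the drug is not there. Its status is therefore missing from the place where this protocol normally states it. Someone who enrolled because they did not want the drug is the very person the exemption omits. Eligibility and care after ablation are protocol matters, so a separate SAP would not settle the point.

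Much of this stands. The word *required* is poorly chosen next to item 1, and no passage covers a refusal.

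The consequences are weaker. Removal for non-compliance is at the investigator's discretion and needs significant non-compliance. The safety text is not confined to the scan: adverse events are assessed to 30 days after ablation, Safety Management follows all related serious events to resolution or stabilization, and Adverse Event Reporting covers unanticipated problems related to the research and notable non-serious events. What patients are told about drugs after ablation cannot be judged, because the consent pages are not available here.

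**Conclusion.** The concern identifies a real inconsistency of wording but gives no reason to change the plan. The two sentences address different times and can both be followed for a patient who accepts a limited course. For one who declines, the text is silent. The surrounding sections favour reading the sentence as a description of standard care. On that reading, its absence from the schedule and risk list, and its running past day 30, are not defects.

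The effect on the planned PET and mapping analysis is zero for any number of preference-route patients from 0 to 15, and the only outcome a refusal might influence has no planned analysis. The 26-day overhang (21 to 31 with the window) would count only on the less supported reading.

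This rests on two assumptions: that the 8 weeks start at ablation, and that the standard-care reading is the intended one. If the sponsor did intend a study requirement, the participation, schedule, adverse event and risk sections would not match it, although the PET and mapping results would still be unaffected. Inclusion criterion 1 and the drug sentence have to be reconciled as a matter of wording. Which clinical rule applies is for the sponsor, and nothing in the design or analysis depends on the answer.

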#### Data Collection:

Demographics and data regarding type of cardiac disease will be collected from patients. Electroanatomic PET maps are the main form of data that will be collected during the study.

#### Analysis:

Baseline and demographic characteristics will be summarized.

In addition to the standard clinical analysis of electroanatomic maps, further offline analysis will be performed at the end of the study. This analysis will include fusing them with the PET scans to make correlations as to the physiologic properties of ablation targets. Ablation targets will be classified to three categories:

- 1. Isthmus sites / isthmus site equivalents
- 2. Exit and entrance sites
- 3. Local abnormal electrograms that do not fall under either of the prior two categories

The investigators will try to make correlations between PET uptake values and electroanatomic data obtained during ablation (data regularly obtained during the course of an ablation case including, for example, refractory periods, voltage measurements, roles in VT circuit). These data are not part of the study CRFs and will be evaluated after all participants have completed the study.

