#### Data Management:

Data will be maintained by Mercy Research according to Mercy and Mercy Research policies and procedures. Case Report Forms will be stored on secured computers.

Data will be stored at a Mercy Research office at Mercy Hospital St. Louis.

Investigators will have access to data / images.

Data will be shared between investigators. Unidentified data could be used for publication in peer review journals, etc.

Images and study data will be shared with Washington University investigators. Data of interest from CRFs for completed subjects will be entered into an Excel spreadsheet at the end of the study to create a study dataset to be shared with Washington University investigators. The study dataset will be sent via Mercy Secure File Transfer system. Images may be accessed by the Mercy Principal Investigator using the Washington University Central Neuroimaging Data Archive (CDNA) and may be shared amongst the Washington University and Mercy study teams for analysis in a secure manner, via the Washington University CDNA system, secure email or CD through mail or hand delivery. PET/CT images will not be loaded into patient medical records.

Confidentiality and Privacy:

All data and records generated during this study will be kept confidential in accordance with Institutional policies and HIPAA and subject privacy.

The investigators and other research personnel will not use such data and records for purposes other than study conduct.

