# **Study Merits and Innovation:**

- a. Using CT to perform accurate merging of PET imaging data with the electroanatomic maps routinely used during ablation procedures
- Aims at examining the applicability of cutting edge imaging techniques and agents, to improve techniques used in routine, yet costly, ablation procedures and improve patient outcomes
- c. Will be the first study to obtain [C-11] MHED in patients who already have clinical VT, which might reveal findings that might not be readily apparent in prospective upstream scans reported in recent studies, which could have been obtained years prior to the development of clinical VT.
- d. Examines the distribution and characteristics of sympathetic dysinnervation in non-ischemic cardiomyopathy, which has not been the focus of other of the studies done with myocardial adrenergic receptor imaging with SPECT or PET.
- e. Eventually, findings could be applied in everyday clinical practice, to improve outcomes and improve the understanding of VT.

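### Ablation targets are sorted into three categories in the same end-of-study analysis that fuses the maps with PET, with no order set, so categories needing judgement can be assigned with uptake known.

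*Protocol*

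**What the plan says.** The Analysis section of the protocol adds an end-of-study offline analysis to the usual clinical analysis of the maps. Of this offline analysis it says: "This analysis will include fusing them with the PET scans to make correlations as to the physiologic properties of ablation targets". It continues: "Ablation targets will be classified to three categories". The first category is isthmus sites and their equivalents, the second is exit and entrance sites, and the third is residual: "Local abnormal electrograms that do not fall under either of the prior two categories". The section then plans correlations of PET uptake with electroanatomic data, naming refractory periods, voltage and roles in the VT circuit. It says of those electroanatomic data: "These data are not part of the study CRFs and will be evaluated after all participants have completed the study".

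Four other sections bear on the point:

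- **Study Procedures:** the PET/CT is done up to 21 days before ablation, so the uptake data exist before any target is mapped.
- **Electroanatomic mapping procedure:** "Entrainment mapping of VT will be pursued whenever possible". On merging it says: "Maps will be merged offline after the ablation case has ended, which is typically done on the mapping computers".
- **Data Management:** investigators have access to data and images, and specifically "Images may be accessed by the Mercy Principal Investigator using the Washington University Central Neuroimaging Data Archive". No time limit relative to classification is given. The images are kept out of the patients' medical records.
- **Data Collection:** the main form of data is described as electroanatomic PET maps.

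**The concern.** The category of a target is one of the variables to be correlated with PET uptake, so the two should be determined independently. The protocol's hypotheses create a clear expectation that areas of altered uptake hold critical elements of the VT substrate. A classifier who shares that expectation and can see uptake may settle doubtful sites in the expected direction.

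At stake are the category-by-uptake correlations. They belong to Goal C, which seeks correlations to be taken into later, larger studies, and they bear on the idea in hypothesis 1 that areas of relatively increased uptake mark critical elements of the substrate. Larger later samples would not reveal that the pilot's labels had been influenced.

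**Working it through.** The protocol gives no figure to reproduce on this point. The check is to set the sections side by side.

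**1. Is an order or a masked reading stated anywhere?** No. Analysis lists fusion and classification in adjacent sentences. No section names the classifier, puts classification before fusion, or restricts what the classifier may have seen. That classification belongs to the fused offline analysis is the natural reading of those sentences, not an explicit statement.

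**2. Does any study record fix the category before fusion?** None is required. The circuit-role data are obtained during the case, but they are not on the CRFs and are evaluated only after all participants have finished. The raw observations are dated to the case; assignment to the three categories is not.

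**3. Could the classifier have seen uptake?** Yes, as written. PET comes first (up to 21 days before ablation), and Data Management gives investigators access to the images without a time restriction.

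**4. Which labels need judgement?**

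- Category 1 includes isthmus site equivalents, which the protocol does not define.
- Entrainment is done only where possible, so some roles must be inferred without it.
- Category 3 is defined by exclusion. It adds no judgement of its own but inherits the uncertainty of the other two.
- Isthmus, exit and entrance roles established during the case leave little room.

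**5. Which results are exposed?**

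- *Category against uptake (Goal C; hypothesis 1, critical elements):* exposed, because the label is one side of the correlation.
- *Hypothesis 2:* it says that targets found by conventional mapping are likely to lie in dysinnervated areas. The relevant share is (targets in such areas) / (all targets). Moving a target from one category to another changes neither the numerator nor the denominator.
- *Voltage and refractory period:* these are measured values and do not depend on the category.

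**6. Can the bias be sized?** Take the simplest case: no true association, a share *p* of targets called isthmus, a share *f* of targets open to judgement, and knowledge of uptake moving the probability of that call at those targets by +*d* in high-uptake areas and by −*d* in low-uptake areas. The spurious difference is (*p* + *fd*) − (*p* − *fd*) = 2*fd*. The protocol gives neither *f* nor *d*, nor the number of targets per patient. The difference is zero if either *f* or *d* is zero, and nothing in the document places it above that. What the document does fix is the scope: the category labels of the targets in up to 15 patients.

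**The case against.** The strongest reply is that this is an omission rather than an error. Analysis does not say that targets are classified after fusion, and reading order and masking may be set in an SAP or the Supplemental Imaging Protocol, neither of which is at hand. This stands in part, and it is why the point is offered as an inexpensive improvement that a cross-reference could satisfy. It does not dispose of the point. The protocol itself describes the reading and puts it beside fusion, and it refers to the imaging supplement for imaging and safety details, not for target classification.

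A second reply is that the categories largely follow from roles observed during the case, and that the maps also receive a standard clinical analysis. This stands for sites with a clear role. It leaves isthmus site equivalents and sites without entrainment.

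A reader might also infer more than the documents support:

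- **That the choice of targets is biased by PET.** Ablation is standard of care, targets come from conventional mapping, merging follows the case, and the stated benefit is guidance for future procedures. Viewing PET beforehand is not expressly barred, but nothing suggests that it steers the ablation.
- **That the test of hypothesis 2 is compromised.** As worded, it depends on where targets lie, not on their category.
- **That a fused map exists for each case before classification.** This requires the post-case merge to be the PET merge mentioned under Study Merits and Innovation ("Using CT to perform accurate merging of PET imaging data with the electroanatomic maps routinely used during ablation procedures") and to be done case by case. Analysis places PET fusion at the end of the study, so this route is conjecture, and the point does not need it.
- **That the Principal Investigator classifies after viewing PET.** Data Management permits access; it does not assign that role or that sequence.

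**Conclusion.** The point holds in a limited form. Followed as written, the protocol allows judgement-dependent categories to be assigned with PET uptake known, which could bias the category-by-uptake correlations under Goal C and for the critical-elements part of hypothesis 1. Hypothesis 2 as worded, voltage and refractory period are outside its reach.

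The size of the bias cannot be estimated, and any odds ratio or false-positive rate put on it would come from assumed inputs. The issue is minor: this is a nonrandomized, hypothesis-generating pilot of 15 patients, and a later re-read of stored maps by someone who has not seen the PET could still repair the labels.

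The conclusion rests on reading the classification as part of the fused offline analysis, and on no other study document already fixing the order.

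**What to change.** In **Analysis**, state that each target's location and category are assigned from the electroanatomic data alone, by the mapping investigator before that investigator views the participant's research PET, and are recorded and locked before that participant's map is fused with PET.

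In **Data Management**, state that investigators who classify targets, including the Principal Investigator if in that role, open a participant's research PET only after the lock. Safety reading at the imaging site is unaffected.

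The cost is a sentence or two in each section and one short record per case, about 15 in all, with no added scan or procedure. No extra reader is needed provided the mapping investigator classifies before opening the PET. The downside is that classifying investigators see the research PET later than they otherwise could. If the SAP or the Supplemental Imaging Protocol already sets this order, a cross-reference in Analysis is enough.
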